3 STUDY DESIGN

This is an extension study, to provide continued access to PRO 140 to subjects who complete participation in PRO140_CD02 or CD02_OpenLabel and continue to receive clinical benefit and would require PRO 140 to form a viable regimen, in the opinion of the treating physician. The patient population for this trial is treatment-experienced HIV-infected patients with CCR5-tropic virus who demonstrate evidence of HIV-1 suppression after successfully completed 24 weeks of treatment in the PRO140_CD02 or CD02_Open Label study.

Subjects participating under Protocol versions 1.0-3.0 received 350 mg of PRO 140. Dose was increased from 350 mg to 700 mg weekly to provide maximum viral load suppression in a heavily treatment experienced population to avoid developing resistance to current OBT therapies.

Those that were enrolled under version 1.0-3.0 have the option of remaining on their current dose of 350mg or increasing their dose to 700 mg for the remainder of the trial.

The study is divided into three phases: Screening, Treatment Extension and Follow-up.

Screening Phase begins with signing of Informed Consent and lasts up to 21 days. All subjects will continue taking PRO 140 SC injection in addition to OBT during the Screening Phase.

Subject will enter the Treatment Extension Phase as soon as HIV-1 viral load results are available for review by Investigator. Treatment Extension Phase consists of weekly study treatment injections along with OBT. Study participants will be regularly monitored for viral load and will cease weekly study treatment injections should they experience virologic failure. Virologic failure is defined two consecutive HIV-1 RNA levels ≥ 400 copies/mL.

Note: Subjects will be allowed to continue PRO 140 with existing OBT regimen while waiting for new regimen to be constructed by the Investigator.

Subjects who experience virologic failure at any point during the Treatment Extension Phase will undergo the Virologic Failure (VF) Visit assessments and will be followed up every 4 weeks until viral suppression is achieved (i.e., plasma HIV-1 RNA levels below level of detection) or up to a maximum of 6 months after cessation of therapy if the treating physician does not feel that there is an antiretroviral regimen that will regain full viral suppression. Subjects who do not experience virologic failure, will be followed up every 2 weeks for total of 4 weeks.

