8.7.5.1 Adverse Events

Adverse events will be coded using Medical Dictionary for Regulatory Activities (MedDRA). TEAEs are defined as events with an onset on or after the first treatment. TEAEs will be summarized by treatment group, System Organ Class, and preferred term. The following TEAE summaries will be provided:

- TEAEs by severity grade
- TEAEs by relationship to study treatment.

In addition, separate summaries of SAEs, and AEs resulting in discontinuation of study treatment will be presented.

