2.3 Study Treatment

2.3.1 Treatment Group

This is a single arm study. All eligible subjects will receive PRO 140 SC injection and Optimized Background Therapy . PRO 140 as a 350mg dose (per protocol prior to v4.0) or 700mg (per protocol after v4.0) subcutaneous injection weekly until one of the following occurs:

- Virologic failure
- Consent withdrawn
- PRO 140 is approved
- CytoDyn decides to discontinue its development

NOTE: Subjects enrolled prior to Protocol v4.0 may still be receiving the original 350mg dose and have the option of increasing their dose to 700mg.

Study Drug	Dosage Form	IP concentration	Dosing Frequency and Amount	Route of Administration
PRO 140 350mg	Parenteral solution	175 mg/mL	2 injections of PRO 140 (2 X 1 mL/inj.) for 48 weeks	SC injection
			for 48 weeks	

PRO 140 700mg		Parenteral solution	175 mg/mL	2 injections of PRO 140 (2 X 2 mL/inj.) for 48 weeks	SC injection
---------------	--	---------------------	-----------	--	--------------

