5. ANALYSIS POPULATIONS

5.1 Safety Population

The Safety population is defined as the set of subjects who received at least one dose of PRO 140. This population will be used for the analysis of safety parameters.

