7.2.4.1 Adverse Events

Adverse events will be classified by system organ class and preferred term (PT) according to the most recent MedDRA dictionary.

Since this is an extension of the PRO 140_CD 02 study, all adverse events (AE) that captured in this study will be considered as Treatment Emergent Adverse Events (TEAEs). The following TEAE summaries will be provided, using frequency counts and percentages:

- Overall (i.e., regardless of severity or relationship to treatment)
- By severity grade (mild, moderate, severe, life threatening or death)
- By relationship to study treatment

In addition, separate summaries of SAEs, and AEs resulting in discontinuation of study treatment will be presented.

Unless otherwise specified, at each level of subject summarization, a subject will be counted only once. If there is more than one occurrence of an event, the event of the worst severity or the worst-case relationship category will be summarized.

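### SAP 7.2.4.1 does not say whether AE tables are split by weekly dose, and its once-per-subject percentages have no dose-at-onset rule and no person-time

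*SAP*

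**What the plan says.** Protocol 8.7.5.1: "TEAEs will be summarized by treatment group, System Organ Class, and preferred term". Protocol 8.1, headed Treatment Groups, calls the study single arm. SAP 2.3.1, headed Treatment Group, also says single arm, but then gives "PRO 140 as a 350mg dose (per protocol prior to v4.0) or 700mg (per protocol after v4.0) subcutaneous injection weekly" and sets the two doses out as separate table rows. Under Protocol 3, subjects enrolled under versions 1.0 to 3.0 "have the option of remaining on their current dose of 350mg or increasing their dose to 700 mg for the remainder of the trial".

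SAP 7.2.4.1 classifies AEs by system organ class and preferred term and continues: "The following TEAE summaries will be provided, using frequency counts and percentages". The summaries listed are overall, by severity and by relationship, with separate summaries of SAEs and of AEs leading to discontinuation. Treatment group and dose are not mentioned. The counting rule is that "at each level of subject summarization, a subject will be counted only once", and "If there is more than one occurrence of an event, the event of the worst severity or the worst-case relationship category will be summarized". There is one analysis set (SAP 5.1): "The Safety population is defined as the set of subjects who received at least one dose of PRO 140". SAP 6.7 and 6.8 state that there are no stratification factors and no subgroup or exploratory analyses.

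Treatment has no fixed end (SAP 2.2, Study Duration). AE collection runs to the final study visit (Protocol 9.1.1), which falls after the end of treatment (Protocol 4.3). The exposure summary in SAP 7.1.7 is a listing plus the number and percentage of subjects injected each week.

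**The concern.** The protocol's phrase can mean one column or two, and the SAP, where it should be settled, does not settle it. If the programmer produces one column, each percentage averages over subjects on 350 mg, subjects on 700 mg and subjects who took both, followed for different lengths of time. If the programmer produces two columns, nothing says where a dose-changer's events belong.

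Four of the seven measures in Protocol 8.2 (items 4 to 7), and three of the six in SAP 2.4, are AE or tolerability frequencies. The dose was doubled during the study, so a reader of the report will ask what was seen at each dose. The listings would allow someone to look afterwards, but no tabulation is specified in advance.

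**Working it through.** The documents give no AE rate, dose split, number of dose-changers or treatment duration, so there is no planned figure to reproduce. The check is a text comparison followed by illustrations with assumed inputs.

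**1. Two dose levels exist.** From the volumes in SAP 2.3.1: 2 × 1 mL × 175 mg/mL = 350 mg, and 2 × 2 mL × 175 mg/mL = 700 mg.

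**2. No other section supplies a split.** SAP 5.1 has one population, SAP 6.7 and 6.8 have no strata or subgroups, SAP 7.1.7 does not tabulate by dose, and SAP 9.2 gives table headings only.

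**3. Crude percentages depend on follow-up.** Percentage with an event = 1 − exp(−rate × years). Assume 50 subjects (the protocol's upper limit), 3 years on 350 mg, 1 year on 700 mg, and no dose-changers.
- Equal rates of 0.2 per person-year: 350 mg gives 1 − exp(−0.6) = 45.1%; 700 mg gives 1 − exp(−0.2) = 18.1%.
- 700 mg rate set at 0.4, only to show the range: 350 mg 45.1%; 700 mg 1 − exp(−0.4) = 33.0%.

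| Subjects 350 mg : 700 mg | Pooled, equal rates | Pooled, 700 mg rate 0.4 |
|---|---|---|
| 40 : 10 | 39.7% | 42.7% |
| 25 : 25 | 31.6% | 39.0% |
| 10 : 40 | 23.5% | 35.4% |

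For example, (40 × 45.1 + 10 × 18.1)/50 = 39.7. With equal rates and 1 year of follow-up at both doses, the pooled figure is 18.1% for every split. The spread in the equal-rates column therefore comes from follow-up and dose mix alone. In the last column, the dose with the higher rate has the lower crude percentage (33.0% against 45.1%), so dose columns without person-time could still mislead.

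**4. Dose-changers.** Assume 2 years on 350 mg, then 1 year on 700 mg. The share of subjects with an event whose first event falls on 350 mg is [1 − exp(−0.4)] / [1 − exp(−0.6)] = 0.330/0.451 = 73% at equal rates, and 0.330/0.551 = 60% if the 700 mg rate is 0.4. The worst-severity rule also takes one event from both dose periods combined. Without an onset rule, these events have no defined column.

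**5. Limits of rates by dose.** Suppose there is no dose effect, but the hazard is 0.6 per person-year for 24 weeks and 0.2 afterwards.
- 150 weeks on 350 mg: (0.6 × 24 + 0.2 × 126)/150 = 0.264. A new 700 mg subject at 24 weeks: 0.60. This is a false ratio of 2.3.
- A subject with 48 weeks of 350 mg then 48 weeks of 700 mg: (0.6 × 24 + 0.2 × 24)/48 = 0.40, against 0.20. This is a false halving.

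Precision is also poor. With 25 subjects for 24 weeks, 25 × 24/52.18 = 11.5 person-years; 7 events give 61 per 100 person-years, exact 95% CI 24 to 125. With 25 subjects per dose for 48 weeks, 14 against 7 events give a rate ratio of 2.0, exact 95% CI 0.76 to 5.86.

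**6. Injection-site reactions.** The standard volumes put 175 mg (1 mL) or 350 mg (2 mL) in each injection. Protocol 6.4 also allows 700 mg as four 1 mL doses, again 175 mg each. Dose per site therefore does not separate the two weekly doses.

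**The case against.** The strongest reply is that Protocol 8.1, under the heading Treatment Groups, says single arm, so the protocol's phrase means one column and the SAP has left nothing out. This stands as far as it goes. A reader might infer that the SAP departs from the protocol, but the documents do not prove it, because the protocol never defines treatment group as dose. That the tables pool doses is itself inferred from silence, since full table shells are not given. What survives is the ambiguity: SAP 2.3.1 lists two doses under Treatment Group, and 7.2.4.1 does not say which sense applies.

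A reader might also infer that treating every captured AE as treatment-emergent is a SAP error. It is not. Protocol 8.7.5.1 counts any onset on or after first treatment, with no end date, and Protocol 9.1.1 starts AE reporting at the first extension visit. Nor does everyone have six months of follow-up off drug. Subjects without virologic failure have 4 weeks. The six-month maximum applies only after virologic failure when no suppressive regimen is thought available, and its start point differs between Protocol 4.3 (cessation of therapy) and Protocol 5.1 and Table 4-2 (virologic failure).

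The documents do not support assuming more AEs at 700 mg. Protocol 1.4.2.1, 1.4.2.4 and 1.4.2.6 report no dose-related AE pattern, although at other doses. No inferential statistics are planned for the safety analysis in SAP 7.2.4, and comparing doses is not an objective (Protocol 2). Weekly injection counts can be summed from the table in SAP 7.1.7, but not by dose.

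**Conclusion.** The point holds as a gap in the descriptive AE tables. As written, they mix two weekly doses, dose-changers and unequal follow-up, so they cannot describe AE frequency at either dose, and crude percentages move with follow-up length. The size of any distortion is unknown; the figures above rest on assumed rates and durations and show the mechanism only. If nearly all subject-time is at one dose, the total is close to that dose and little is lost.

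Type I error, power and the access objective are not affected. It would go too far to conclude that a dose effect on AEs exists or is being hidden, or that the revised tables could establish one. This is a cheap improvement.

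**What to change.** In SAP 7.2.4.1, state that TEAEs, Grade 3–4 AEs, SAEs and AEs leading to discontinuation are tabulated by weekly dose at onset (350 mg, 700 mg, total), meaning the weekly dose most recently given before onset. Show subjects, events, person-years and rate per 100 person-years. Dose-changers contribute time to each dose and may be counted in both columns, so columns need not sum to the total.

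In addition:
- Add person-years by weekly dose to SAP 7.1.7.
- Show events after the last injection separately. The sponsor should set the on-treatment window and justify it from PRO 140 persistence data, not from the visit interval. Protocol 1.4.2.4 and 1.4.2.5 report receptor effects lasting 2 to 4 weeks, and 29 days, after single IV doses. The weekly interval plus the 3-day visit window is only 10 days.
- Summarise injection-site reactions per clinic assessment by the weekly dose assigned at that visit, not by dose per site.
- State that these tables are descriptive and non-randomised, that dose is confounded with time in study and protocol version, that rates assume a roughly constant hazard, and that no dose difference is tested.

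Before the dose variable is derived, two contradictions must be reconciled. First, SAP 7.1.7 gives 350 mg weekly, then a total of 700 mg, and describes subjects still on 350 mg as enrolled under version 4.0, whereas SAP 2.3.1 describes them as enrolled before it. Second, the dose table in SAP 2.3.1 gives 48 weeks, whereas treatment is otherwise open-ended.

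The cost is SAP text and extra table columns, with no new visits. First confirm that the dose and date of each injection are captured; SAP 7.1.7 gives no field list. The downside is small cells with wide intervals, as shown above.

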7.2.4.2 Tolerability Assessment

7.2.4.3 Injection Site Reaction

At each visit during the Treatment Extension Phase, an injection site reaction assessment will be made for the current and previous injection sites. Injection site reaction assessments are recorded by the Investigator starting after the first injection is given. All data from the injection site reaction assessments of the repeated subcutaneous administration of PRO 140 will be presented and descriptively summarized.

7.2.5 Clinical Laboratory Evaluations

All available results of the clinical laboratory evaluations will be listed and summarized. Laboratory evaluations include hematology (routine CBC), biochemistry, coagulation indices, urinalysis, glomerular filtration rate (GFR) and HBsAg etc.

7.2.5.1 Laboratory Values over Time

Summary statistics of raw data and change from baseline values for each laboratory parameter will be presented. Data will be summarized as appropriate to the variable type.

For change from baseline summaries, subjects with an undefined change from baseline, because of missing data, will be excluded.

7.2.5.2 Individual Subject Changes (Shift Tables)

Individual subject changes will be identified through shift tables. Shift tables will be presented for each laboratory parameter with counts and percentages of subjects, for shift (change) from baseline.

7.2.6 Physical Examination

All physical examination findings will be listed and/or summarized.

7.2.7 Vital Signs

Tabulations of raw data and change from baseline values will be presented by time point for each vital sign parameter [*i.e.*, Heart Rate (beats/min), temperature ($^{\circ}\text{C}$ / $^{\circ}\text{F}$), systolic BP (mmHg), diastolic BP (mmHg), and Respiration Rate].

Tabulations will include the number of observations, mean, standard deviation, median, and minimum and maximum values. For change from baseline summaries, subjects with an undefined change from baseline, because of missing data, will be excluded.

7.2.8 Electrocardiogram (ECGs)

All ECGs findings will be listed and/or summarized. The following parameters will be recorded: ventricular rate (beats per minute), PR interval (msec), QRS interval (msec), QT interval (msec), and QTc interval (msec). Additionally, the investigator will record the overall results of the ECG reading as either normal or abnormal, and as either not clinically significant or clinically significant. If abnormalities are observed, each will be recorded.

7.2.9 Additional Data listings and tabulations

7.2.9.1 *Neurological Assessment*

All neurological assessment results will be listed and any abnormality will be summarized.

7.2.9.2 *Urine Pregnancy Test*

All the results from urine pregnancy will be presented as a by-subject listing.

7.2.9.3 *Notification and Outcome Pregnancy*

All the results for Notification and Outcome Pregnancy will be presented as a by-subject listing.

7.2.9.4 HIV-1 Trofile® DNA/RNA Assay and Drug Resistance, Genotypic and Phenotypic data

Data for HIV-1 trofile® DNA/RNA assay as well us Drug Resistance, Genotypic and Phenotypic data will be provided by external vendor Monogram Biosciences. All data will be presented as by-subject listings.

7.2.9.5 TruCount Assay (including CD4 Counts)

Data for TruCount assay will be provided by external vendor Covance. All data will be presented as by-subject listings.

8. APPENDIX 1: SCHEDULE OF ASSESSMENTS

TABLE 1: SCHEDULE OF ASSESSMENTS – SCREENING AND TREATMENT PHASE

Procedure/Assessments	Screening	Treatment Phase						
		Visit	Screening (T23/24/25)	(EOT)	TE1 ^b	Subsequent TE Visits (weekly ±3 days)	EOT	VF
				Pre-treatment	Post-treatment			
Informed Consent ^[1]	X							
Subject Demographics	X							
Medical & HIV History ^[2]	X							
Eligibility	X		X					
Physical Examination	X ^[3]		X ^[3]			X ^[3]	X	X ^[3]
Neurological Examination ^[4]	X		X				X	X
Vital Signs ^[5]	X ^[3]		X ^[3]	X		X	X	X
ECG	X						X	
Complete Blood Count ^[6]			X ^[3]			X ^[15]	X	X
Biochemistry ^[7]			X ^[3]			X ^[15]	X	X
Coagulation ^[8]			X ^[3]			X ^[15]	X	X
Urinalysis ^[9]			X ^[3]			X ^[15]	X	X
Urine pregnancy test ^[10]			X					
Plasma HIV-1 RNA level ^[11]	X		X			X	X	X
TruCount T assay ^[11]	X		X			X	X	X
PRO 140 + OBT Regimen	X		X			X	X	
Injection Site Reaction Assessment - Investigator ^[12]		X		X		X	X	
HIV-1 T-Profile® RNA + PhenoSense Entry Assay ^[13]								X
HIV-1 Drug Resistance Assay ^[14]								X
Adverse Events	X			X		X	X	X
Concomitant Medications	X		X			X	X	X

X (red bold with yellow highlight): Activities performed under PRO 140_CD02 study protocol

^a Schedule of assessment (Screening/Treatment Phase) can be modified by the Investigator based on clinical judgment and in the best interest of the subject.

^b Subject eligibility should be confirmed prior to study treatment administration at TE1.

Foot Notes:

- [1] Informed consent must be obtained prior to subject participation in any protocol-related activities that are not part of routine care.
- [2] Medical history, past surgeries, disease history, history of substance abuse, social history, blood transfusion history, and current therapies (medications and non-medications) will be brought forward from PRO140_CD02.
- [3] Symptom-directed physical examination. Complete physical examination at TE1, EOT2 and VF.
- [4] The screening tool for this assessment is based on the three question survey used by Simioni et al. (Simioni S, 2010). Additional modalities may be used for this assessment at the discretion of the Investigator.
- [5] Vital signs (i.e., blood pressure, heart rate, respiration rate and temperature) will be recorded post-treatment whenever IP administered at the clinic.
- [6] Hemoglobin, Hematocrit (HCT), Red Blood Cells (RBC), White Blood Cells (WBC) with total and differential count, Absolute Neutrophil Count (ANC) and platelets.
- [7] Serum Biochemistry
Hepatic function indicators: total and direct bilirubin, alkaline phosphatase, aspartate aminotransferase (AST), alanine aminotransferase (ALT), total protein, Lactate dehydrogenase (LDH)
Renal function indicators: BUN, creatinine
Electrolytes: sodium, potassium, chloride, calcium and bicarbonate
Other: glucose (random), cholesterol (total)
- [8] Prothrombin time (PT) and International Normalized Ratio (INR)
- [9] Urine samples will be tested for color, appearance, specific gravity, pH, protein, glucose, occult blood, ketones, leukocyte esterase, nitrite, bilirubin, urobilinogen, and microscopic examination of urine sediment.
- [10] ONLY performed on women of childbearing potential. Subject will not be allowed to participate if the result is positive.
- [11] Plasma HIV-1 RNA and TruCount T Assay will be performed once every 4 weeks when subject comes to clinic. TruCount T Assay includes: CD3 %, CD4 %, CD8 %, Absolute Lymphocytes, CD3 cell count, CD4 cell count, and CD8 cell count
- [12] Injection Site Reaction will be assessed by the Investigator whenever IP administered at the clinic.
- [13] Monogram Biosciences Trofile® RNA and PhenoSense® Entry Assays [AMD3100 (CXCR4 inhibitor drug), Maraviroc and PRO 140 (CCR5 inhibitor drugs)]
- [14] Monogram Biosciences PhenoSense® GT Assay
- [15] Every 12 weeks during Treatment Extension.

TABLE 8-2: SCHEDULE OF ASSESSMENTS – FOLLOW-UP (FU) PHASE

(a) Subjects who do NOT experience virologic failure

Procedure/Assessments	Follow-Up Visit -1	Follow-Up Visit -2
	NVF-EFU1	NVF-EFU2
Window Period	2 weeks (±3 days) after EOT2 visit	4 weeks (±3 days) after EOT2 visit
Physical Examination	X ^[1]	X ^[1]
Vital Signs	X	X
Plasma HIV-1 RNA level	X	X
TruCount T assay	X	X
Adverse Events	X	X
Concomitant Medications	X	X

[1] Symptom-directed physical examination

(b) Subjects who experience virologic failure

Procedure/Assessments	Follow-Up Visit -1	Follow-Up Visit -2	Follow-Up Visit -3 ^[1]
	VF-EFU1	VF-EFU2	VF-EFU3
Window Period	4 weeks (±7 days) after VF visit	8 weeks (±7 days) after VF	12 weeks (±7 days) after VF
Physical Examination	X ^[2]	X ^[2]	X ^[2]
Vital Signs	X	X	X
Plasma HIV-1 RNA level	X	X	X
TruCount T assay	X	X	X
Adverse Events	X	X	X
Concomitant Medications	X	X	X

- [1] Subject will be followed up till the viral suppression is achieved or up to a maximum of 6 months after experiencing Virologic Failure (VF) if the treating physician does not feel that there is an antiretroviral regimen that will regain full viral suppression.
- [2] Symptom-directed physical examination

9. APPENDIX 2 – PLANNED TLG

9.1 Planned by-subject listings

DISPOSITION/WITHDRAWALS (LISTINGS 16.2.1.X)

ELIGIBILITY AND PROTOCOL DEVIATIONS (LISTINGS 16.2.2.X)

EXCLUDED SUBJECTS (LISTINGS 16.2.3.X)

DEMOGRAPHICS, POPULATION, AND BASELINE CHARACTERISTICS (LISTINGS 16.2.4.X)

TREATMENT ADMINISTRATION LISTINGS (LISTINGS 16.2.5.X)

EFFICACY RESPONSE DATA (LISTINGS 16.2.6.X)

ADVERSE EVENT DATA (LISTINGS 16.2.7.X)

SAFETY DATA (LISTINGS 16.2.8.1.X)

9.2 Planned Summary Tables

POPULATION DISPOSITION AND PROTOCOL DEVIATIONS

POPULATION DEMOGRAPHICS AND BASELINE CHARACTERISTICS

CONCOMITANT MEDICATION USAGE

EFFICACY SUMMARIES

SAFETY SUMMARIES

ADVERSE EVENT SUMMARIES

SERIOUS ADVERSE EVENTS

LABORATORY

VITAL SIGNS AND PE

OTHER SAFETY

11. VERSION HISTORY

This is the first version of the document.
